### 7.8.2 Secondary Endpoints

The following secondary endpoints will be evaluated in all enrolled subjects:

- Number of cases that are technically successful (successful completion of local registration), define as,
  - In 'LESN\_CHAR' CRFThe technically successful is defined as that 'Was local registration successful' is checked 'YES'. The results will be summarized using frequency measures in the format of p% (x/N), with x being the number of lesions with successful completion of local registration and N being the number of lesions undergo the procedure.
- In cases that are not technically successful, reason for incomplete local registration in each target lesion, define as,
  - In 'LESN\_CHAR' CRFIf 'Was local registration successful' is checked 'NO', list all detail from 'If No, provide reason'.

- Investigator confirmation that the catheter is in an “Adequate Periprocedural Location” (the location of the extended working channel with the proceduralist makes the decision that placement is adequate and clinically acceptable to proceed with tissue sampling), define as,
  - In ‘LESN\_CHAR’ CRF

If ‘Adequate Periprocedural Location’ is checked ‘YES’. The results will be summarized using frequency measures in the format of p% (x/N), with N being the number of lesions undergoing the procedure.

- Total procedure time, define as,

In ‘PROC’ CRF, first entry of the bronchoscope to the last exit of the bronchoscope

- ENB procedure time, define as,

In ‘PROC’ CRF, total time from the first entry of the extended working channel or locatable guide until the last exit of the extended working channel.

- Total fluoroscopy time, as measured by the fluoroscopy system, define as,

In ‘PROC’ CRF, ‘What was the total fluoroscopic time’ will be summarized using the descriptive statistics.

- Adequacy of the ENB-aided tissue sample for rapid on-site evaluation (ROSE) of cytologic samples by pathology (when applicable)

In ‘DIAG’ CRF, if ‘ROSE Diagnosis’ is not checked ‘INADEQUATE TISSUE FOR ROSE’.

- Histopathological call based on ROSE of the ENB-aided tissue sample (when applicable)

In ‘DIAG’ CRF, ‘ROSE Diagnosis’ will be summarized using the descriptive statistics of categorical variables.

- Final pathology results of the ENB-aided tissue sample

In ‘DIAG’ CRF, ‘Pathology Diagnosis’ will be summarized using the descriptive statistics of categorical variables.

- Biopsy tools used, tool order, number of passes, and final pathology of the ENB-aided sample

In ‘DIAG’ CRF, ‘Tool Name’, ‘Tool Order’ and ‘Number of Passes’ will be summarized using the descriptive statistics or data listing.

In Technically Successful cases (local registration complete):

- Percentage of cases in which the intended lesion is correctly identified (as opposed to a nontarget lesion or normal lung tissue) as indicated by the system software.

In MUO CRFs, 'Was the target/planned lesion correctly marked by the physician?' will be summarized using the descriptive statistics to present the count and percentage.

- Relational Accuracy in cases in which the Intended lesion is targeted.

Relational accuracy, defined per protocol as the three-dimensional relationship between the catheter and the lesion in terms of distance and vector, was calculated as the three-dimensional percentage overlap between the virtual target and the actual lesion in CBCT.

In MUO CRFs, 'Calculated Percent Overlap' will be summarized using descriptive statistics.

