[name]
[name]
[name]
USA
www.medtronic.com

Official Title: A Post-market Feasibility Study Evaluating Location Accuracy Using the superDimension™ Navigation System Version 7.2 With Fluoroscopic Navigation Technology in Subjects Undergoing Lung Lesion Biopsy

ClinicalTrials.gov ID: NCT03585959

Date of Document: 05Dec2019

Note to File Fluoroscopic Navigation Study

GBET-091

v2

Page 1 of 2

Global
Business
Efficiency
Tool
Medtronic

Note to File

Study name:	MDT18004ILSFNV (Fluoroscopic Navigation Clinical Study)	Investigation Site Name/ Number (if applicable):	N/A
Subject:	Fluoroscopic Navigation Clinical Study Inclusion/Exclusion Criteria CIP Typos		

Prepared by	[name]
Date of preparation	20 Nov 2019
Document	Fluoroscopic Navigation CIP_Final_v1.0_09Apr18

This Note to File is to document typos in the inclusion and exclusion criteria of the Clinical Investigation Plan (CIP) for the Fluoroscopic Navigation Clinical Study.

On 18Sep19 the ILS Medical Writer identified a typo in the CIP for the Fluoroscopic Navigation Clinical Study regarding the Exclusion Criteria 1. The word "not" was included in error:

Central lesions that are **not** visible endobronchially or could be reached by a flexible bronchoscope or endobronchial ultrasound (EBUS) without utilization of ENB

Exclusion Criteria 1 should have stated: *re [name] 5Dec2019*

Central lesions that are **not** visible endobronchially or could be reached by a flexible bronchoscope or endobronchial ultrasound (EBUS) without utilization of ENB

On 29Oct19, a site Principal Investigator noticed that Inclusion Criteria 1 inaccurately states the targeted lesion size for potential subjects:

Subjects presents with lung lesion(s) greater than 10 mm in diameter amendable to evaluation by the ENB at the time of the evaluation

Inclusion Criteria 1 should have stated:

Note to File Fluoroscopic Navigation Study

GBET-091

[figure not shown]
v2

Page 2 of 2

Global
Business
Efficiency
Tool
Medtronic

Subjects presents with lung lesion(s) greater than **or equal to** 10 mm in diameter amendable to evaluation by the ENB at the time of the evaluation

The intent of the inclusion criteria was to be consistent with the superDimension Indications for Use.

The CIP will not be updated as the study has been closed by the sponsor and the Site IRBs.

Name: [name]	Role: Clinical Study Manager
Signature:	Date: 12/01/2019 (dd/mmm/yyyy)

Approved by:

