### 5. Investigation Plan

This post-market feasibility study is planned in up to 50 subjects meeting the inclusion criteria and undergoing elective ENB with the superDimension™ Navigation System v7.2 with Fluoroscopic Navigation Technology. The study will confirm the location accuracy of the optional local registration feature. Enrolled subjects will first undergo a standard ENB procedure to navigate to within 2.5 cm of the target lesion. Local registration with Fluoroscopic Navigation Technology will be conducted and fluoroscopy and CBCT scans will be used to document that the biopsy tool location accuracy.

Periprocedural endpoints include confirmation of accurate positioning of the virtual target (representing the target lesion), technical success, relational accuracy, adequate periprocedural location, procedure time, adequacy of tissue captures for pathology, tool usage, and histopathological results. Safety will be evaluated immediately post-procedure and 4-7 days post-procedure.

This study will be conducted in subjects over the age of 18 undergoing elective biopsy of lung lesions greater than 10 mm in diameter. Additional inclusion/exclusion criteria are listed in CIP section 8.3 and 8.4.

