## 7.4 Handling of Missing, Unused, and Spurious Data and Dropouts

Due to the post-market and observational nature of the study, no imputation is planned for missing data in the primary and secondary endpoints, if any. All available data from enrolled subjects will be reported.

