## 7.8 Evaluation of Objectives

### 7.8.1 Primary Endpoint

The Primary Endpoint is the measured ability of the superDimension™ Navigation System v7.2 with Fluoroscopic Navigation Technology to place the center of the virtual navigation target (green ball) on the intended target lesion as confirmed by CBCT.

The primary endpoint will be evaluated in Technically Successful cases (local registration complete) and calculated as the number and percentage of cases in which the center of the virtual target was correctly placed to overlap the target lesion in coronal view, as confirmed by CBCT. In 'MUO\_IMAG' CRF, the subject meets the primary endpoint if 'Target Overlap in Coronal View' is checked 'Yes'.

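### Does the ROSE adequacy endpoint need a stated unit, denominator and rule for blank entries?

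*SAP*

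**What the plan says.** SAP section 7.8.2 lists, among the secondary endpoints for all enrolled subjects, adequacy of the tissue sample "for rapid on-site evaluation (ROSE) of cytologic samples by pathology (when applicable"). The whole derivation is that the sample counts as adequate "if ‘ROSE Diagnosis’ is not checked ‘INADEQUATE TISSUE FOR ROSE".

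Other text that bears on the unit, the denominator and missing entries:

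- Section 7.8.2 gives technical success and adequate periprocedural location as a percentage with x/N. For the latter it says "with N being the number of lesions undergoing the procedure".
- Section 7.8.1 speaks of cases and then says "the subject meets the primary endpoint if" the overlap box is ticked, so its wording mixes units.
- Section 7.8.2 takes the tool data from the same DIAG form: "Tool Name’, ‘Tool Order’ and ‘Number of Passes’ will be summarized". The final pathology diagnosis also comes from DIAG.
- The bullet after ROSE adequacy tabulates the same ROSE Diagnosis field as a categorical variable. Section 7.2 says such variables get frequencies and percentages.
- Section 7.4 says "no imputation is planned for missing data in the primary and secondary endpoints, if any" and that available data will be reported.
- Section 5 names "adequacy of tissue captures for pathology" among the periprocedural endpoints.
- The Note to File in the Protocol document cites inclusion criterion 1 as "Subjects presents with lung lesion(s) greater than 10 mm in diameter". The note corrects the size limit, but the plural that allows more than one lesion stays.

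**The concern.** The rule is worded as a negation. Technical success and adequate periprocedural location need a positive tick, so an empty field cannot count as success there. Here, read literally, an empty ROSE Diagnosis does count as adequate.

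The unit is the larger question. DIAG carries tool order, which has meaning only if more than one tool can be recorded. If ROSE Diagnosis were also entered once per tool, the rule could be read in three ways:

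- (a) the share of entries that are not inadequate;
- (b) the share of lesions with at least one entry that is not inadequate;
- (c) the share of lesions with no inadequate entry.

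Two analysts could then report different percentages from the same data. A reader given only a percentage could not reproduce it, and a programmer doing the peer check in SAP section 8 would have no written rule to check against.

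**Working it through.** The plan states no figure for ROSE adequacy, and section 6 says the sample size is not based on power, so there is nothing to reproduce. Every count below is an assumption chosen to show how the readings behave.

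**Several entries per lesion.** Assume 30 lesions with ROSE, two entries each (60 entries), and 12 inadequate entries. Let k be the number of lesions with both entries inadequate; then 12 − 2k lesions have exactly one.

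- (a) = (60 − 12)/60 = 48/60 = 80%
- (b) = (30 − k)/30
- (c) = (30 − k − (12 − 2k))/30

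| k | (a) | (b) | (c) | (b) − (c) |
|---|---|---|---|---|
| 0 | 80% | 30/30 = 100% | 18/30 = 60% | 40 points |
| 3 | 80% | 27/30 = 90% | 21/30 = 70% | 20 points |
| 6 | 80% | 24/30 = 80% | 24/30 = 80% | 0 points |

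A second assumed data set has 40 lesions with ROSE: 15 with two adequate entries, 10 with one of each, 5 with two inadequate, and 10 with a single adequate entry.

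- (a) = (30 + 10 + 0 + 10)/70 = 50/70 = 71.4%
- (b) = (15 + 10 + 10)/40 = 35/40 = 87.5%
- (c) = (15 + 10)/40 = 25/40 = 62.5%

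**Order of the readings.** (b) is never below (c). It can fall below (a) when lesions have unequal numbers of entries. One lesion with nine adequate entries and one with a single inadequate entry give (a) = 9/10 = 90% and (b) = 1/2 = 50%.

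**One entry per lesion.** The three readings coincide. Only the choice between subject and lesion stays open, and that makes no difference where each subject has one lesion.

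**Blank entries.** Assume 30 lesions with ROSE performed, one entry field each, 6 recorded inadequate and b left blank. The literal rule gives (30 − 6)/30 = 80.0% whatever b is. Using recorded entries only gives (30 − b − 6)/(30 − b):

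| b | Recorded only | Difference from 80.0% |
|---|---|---|
| 0 | 24/30 = 80.0% | 0 |
| 1 | 23/29 = 79.3% | 0.7 points |
| 2 | 22/28 = 78.6% | 1.4 points |
| 3 | 21/27 = 77.8% | 2.2 points |

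**Cases without ROSE.** Suppose the 40 lesions of the second data set come from 50 subjects with one lesion each, 10 of them without ROSE. Keeping those 10 in the denominator gives 25/50 = 50% under (c). Counting them as adequate gives (35 + 10)/50 = 90% under (b). The qualifier limiting the endpoint to applicable cases rules out both, so neither figure measures the gap.

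**The case for a change.** The strongest case for a change is that the omission is not the SAP's general habit. It names the lesion as denominator twice in the same list, separates subject-based from lesion-based characteristics in section 7.7, and reports both events and subjects in sections 7.1.2 and 7.9. Naming all enrolled subjects fixes a population, not a unit of count. Tissue adequacy is a listed endpoint, and one or two sentences would settle the matter without new data.

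The textual point stands: the definition is incomplete. The rest carries less weight:

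- Sharing a form with tool data does not show that ROSE Diagnosis repeats by tool. Final pathology sits on the same form, and the endpoint speaks of the tissue sample in the singular. The form itself is not in the documents.
- Counting an empty diagnosis as adequate would in effect impute a result, which section 7.4 excludes.
- The table of ROSE diagnoses under the next bullet would ordinarily show the inadequate count and its total, so the rate should not be left wholly opaque, although the unit is unnamed there too.
- Writing reading (b) into the SAP would be a preference with no basis in the documents, and it is the more generous of the two lesion-level rules.

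**Conclusion.** No change to the plan follows. This is unwritten detail in a descriptive secondary endpoint of a feasibility study; it feeds no decision rule, hypothesis test or sample size and leaves the primary endpoint alone. A sensible analyst would count lesions, as the neighbouring endpoints do, and would leave out cases without ROSE and blank diagnoses.

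The one reading that could matter depends on several ROSE entries per lesion, which no document states. If they exist, the lesion-level readings can differ widely (0 to 40 points on one set of assumed counts). If there is one mandatory entry per lesion, only the choice between subject and lesion remains. Blanks are worth about 2 points at most in the cases worked above.

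The Note to File says that the sponsor and the site review boards have closed the study and that the clinical investigation plan will not be updated, so rewording the SAP would gain little. Ordinary reporting covers what is left: show the count and denominator beside the percentage, and say which unit and combining rule were used and how many ROSE results were not done or missing.

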## 7.9 Safety Evaluation

The following safety endpoints will be evaluated in all enrolled subjects. These events will be evaluated for their relationship to the study device and study procedure, and classified according to Common Terminology Criteria for Adverse Events (CTCAE) Version 5.

- Incidence of all pneumothorax related to ENB index procedure
- Incidence of CTCAE Grade  $\geq 2$  pneumothorax related to the ENB index procedure
- Incidence of all bronchopulmonary hemorrhage related to ENB index procedure
- Incidence of CTCAE Grade  $\geq 2$  bronchopulmonary hemorrhage related to the ENB index procedure
- Incidence of CTCAE Grade  $\geq 4$  respiratory failure related to ENB index procedure

In addition to the Safety Endpoints described above, all Adverse Events related to the superDimension™ navigation system, associated tools, or ENB procedure as described in CIP Section 11 will be collected for all enrolled subjects. Summary of overall event, events relatedness, seriousness and severity will be provided. To assess safety, the number and percentage of subjects with adverse events will be summarized and the number of events will be provided for each category as well.

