### 7.1.3 Analysis Sets

- Enrolled subjects

Subjects meeting the inclusion/exclusion criteria will be enrolled. Following signing the informed consent form (ICF), the point of enrollment is defined as the entry of the first locatable guide.

- Technically Successful cases

Successful completion of Local Registration utilizing Fluoroscopic Navigation Technology in superDimension™ Navigation System Version 7.2.

The following study endpoints will be evaluated in Technically Successful cases:

- Primary endpoint
- Secondary endpoints:
  - Percentage of cases in which the intended lesion is correctly identified (as opposed to a non-target lesion or normal lung tissue) as indicated by the system software.
  - Relational Accuracy in cases in which the Intended lesion is targeted.

All other endpoints and safety outcomes will be evaluated in all enrolled subjects.

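### All five safety endpoints in SAP 7.9 count only events attributed to the index ENB procedure, and no any-cause count is planned beside them

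*SAP*

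**What the plan says.** SAP 7.9 (Safety Evaluation) lists five endpoints: pneumothorax of any grade and of CTCAE Grade 2 or higher, bronchopulmonary hemorrhage of any grade and of Grade 2 or higher, and respiratory failure of Grade 4 or higher. Each carries the same restriction. The two broadest read "Incidence of all pneumothorax related to ENB index procedure" and "Incidence of all bronchopulmonary hemorrhage related to ENB index procedure"; the last is limited to "respiratory failure related to ENB index procedure". The word *all* in the first two therefore refers to grade, not to cause.

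The section introduces the endpoints by saying that "These events will be evaluated for their relationship to the study device and study procedure". Beyond the endpoints, it says that "all Adverse Events related to the superDimension™ navigation system, associated tools, or ENB procedure as described in CIP Section 11 will be collected". For reporting it promises: "Summary of overall event, events relatedness, seriousness and severity will be provided". The unit is subjects, with event counts added: "the number and percentage of subjects with adverse events will be summarized and the number of events will be provided for each category as well".

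SAP 7.1.3 sets the denominator: "All other endpoints and safety outcomes will be evaluated in all enrolled subjects". SAP 6 caps enrollment at 50, with no power calculation behind that figure. Table 1 in SAP 7.1.1 schedules an adverse event assessment on Day 0 and at the 7-day contact (window 4-7 days), with no mention of relatedness. The note to file in the Protocol document states that the study has been closed and that the CIP will not be updated.

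**The concern.** Relatedness can enter a safety analysis in two ways. It can be a field recorded for every event, so that any-cause and related rates can both be tabulated. Or it can be part of the definition of what counts, so that only the related rate appears. SAP 7.9 takes the second route for its endpoints, and its one sentence on adverse event collection is also worded around related events.

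The SAP describes a single group, so no comparator rate exists against which a pattern of attribution could be checked, and the available text names no independent adjudication of relatedness. If a respiratory or bleeding event in the days after a lung biopsy is put down to something other than the procedure, it drops out of the endpoint. With no any-cause figure beside it, nobody reading the report can see that this happened or how often.

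The section also does not read as one rule. It plans to evaluate relationship and to summarize events overall and by relatedness, yet its definitions and its collection sentence already assume that relatedness has been decided.

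**Working it through.** **Inputs.** Endpoint definitions, collection sentence and planned summaries: SAP 7.9. Safety set, all enrolled subjects: SAP 7.1.3. Maximum N = 50: SAP 6. Timing of assessments: SAP 7.1.1, Table 1. The documents give no expected or observed safety rate, so there is no stated figure to reproduce.

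**Step 1: the passages side by side.**

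| Element | Limited to related events? |
|---|---|
| Five endpoint definitions (7.9) | Yes, all five |
| Collection sentence for further adverse events (7.9) | Yes as worded, but it defers to CIP Section 11 |
| Evaluation of endpoint events for relationship (7.9) | No; suggests events are identified before they are attributed |
| Overall and relatedness summary (7.9) | Not stated |
| Scheduled assessment (Table 1) | No |
| Any-cause incidence | Not planned anywhere in the available text |

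The first and last rows do not depend on CIP Section 11. The question of what was recorded does.

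**Step 2: how attribution enters the rate.** Let T be the number of subjects whose event is truly related, f the number of those called unrelated, and g the number with a truly unrelated event called related. Then

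reported rate = (T - f + g) / N.

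The error is (g - f)/N and can go either way. An any-cause rate does not depend on f or g.

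**Step 3: size of one reclassification.** One subject is worth 1/N. At the maximum N = 50 this is 1/50 = 2.0 percentage points. With fewer enrolled it is larger; at N = 25, for example, it is 1/25 = 4.0 points. So 2 points is the minimum.

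**Step 4: illustration at N = 50.** The counts are assumed, not taken from the documents. The exact (Clopper-Pearson) 95% limits for x of n are the 2.5% point of Beta(x, n - x + 1) and the 97.5% point of Beta(x + 1, n - x); the lower limit is 0 when x = 0.

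| Any-cause | 95% CI | Judged related | 95% CI | Difference |
|---|---|---|---|---|
| 1/50 = 2.0% | 0.1-10.6 | 0/50 = 0% | 0-7.1 | 2.0 points |
| 3/50 = 6.0% | 1.3-16.5 | 2/50 = 4.0% | 0.5-13.7 | 2.0 points |
| 4/50 = 8.0% | 2.2-19.2 | 2/50 = 4.0% | 0.5-13.7 | 4.0 points |

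The intervals are wide, so a shift of this size lies within sampling uncertainty. It is not sampling error, however, and an interval around the related rate does not account for it. In the first row, one judgement decides whether the report shows an event or none.

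**The case against.** The strongest reply is that the operative rule for adverse event collection is in CIP Section 11, to which the SAP sentence defers, and that a section not available for review cannot be counted as a gap in the plan. The SAP's own text also points partly the other way. The collection sentence is introduced as an addition to the safety endpoints, so it governs other adverse events; no sentence sets a collection limit for the three endpoint event types. Evaluating those events for relationship suggests that they are captured first and attributed second, and Table 1 has an unrestricted assessment. All of this stands. A reader might infer that an event attributed elsewhere leaves no record; the documents do not establish that.

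A reader might also infer that a set limited to related events makes the relatedness summary impossible. It does not: 7.9 names several possible causes, and events could still be tabulated by device, tool and procedure. An unrelated category would be missing only if collection was in fact limited.

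A third tempting inference is that misattribution can only lower the rates. Step 2 shows that it can also raise them.

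Finally, this is an unpowered feasibility study whose primary objective is location accuracy, and the endpoint names disclose the restriction openly. That is fair and argues for a modest weight. It does not supply an any-cause count, whose absence is clear from 7.9 whatever CIP Section 11 says.

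**Conclusion.** The point holds in limited form. All five safety endpoints depend on an attribution judgement, and the SAP plans no any-cause figure that would let a reader see its effect. One reclassified subject moves a rate by at least 2 percentage points at the planned maximum of 50, and a related event called unrelated would reduce the reported rate without any sign in the planned tables. The actual effect is unknown and could be zero, since the documents give no event counts.

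The wording of 7.9 should also be reconciled. Collection phrased around related events sits awkwardly beside a plan to evaluate relationship and to summarize events overall, although this is an ambiguity and not a proven contradiction.

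The conclusion assumes that CIP Section 11 does not itself call for any-cause reporting of these events, and that the denominator is all enrolled subjects. It is a cheap improvement that should be made; it does not touch the primary endpoint.

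**What to change.** **In SAP 7.9:** state that every pneumothorax, bronchopulmonary hemorrhage and CTCAE Grade 4 or higher respiratory failure, from the start of the index procedure to the last study contact, is recorded whatever its attributed cause, with relatedness as a field. For each of the five endpoints, report any-cause incidence beside related incidence in all enrolled subjects.

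**Because the study is closed:** check CIP Section 11 and the database for what was recorded. If unrelated events of these three types are there, report both rates and document the change under SAP 7.11. If it is confirmed that they were not recorded, label the safety tables as covering events judged related only. That label should not be applied on the strength of the SAP wording alone.

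**Cost:** one extra table column and, had the rule been set prospectively, a few more adverse event entries in at most 50 subjects. The published rates may look less favourable.
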